6.15.2. Adverse Events

Adverse events (AEs) will be classified based upon the latest version of the MedDRA. Adverse events will be recorded at every study visit. Any untoward condition starting on or after the date of informed consent will be considered an AE. Any pre-existing condition which worsens in severity on or after the date of informed consent will be considered and recorded as an AE on the AE eCRF page from the date of worsening onwards.

A treatment-emergent adverse event (TEAE) is defined as an AE that first occurred or worsened in severity after baseline and on or prior to the date of the last visit within the defined treatment period. Both the date/time of the event and the date/time of the dose (that is, injection) are considered when determining TEAEs. Treatment-emergent AEs will be assigned to the respective study periods in which they are considered treatment-emergent.

The MedDRA lowest level term (LLT) will be used when classifying AEs as treatment-emergent.

- The maximum severity recorded for each LLT prior to the first dose date/time in the treatment period will be used as the pre-treatment severity for that LLT. If an event during the baseline period has missing severity, and the event persists during the treatment period, then it will be considered as treatment-emergent, regardless of the post-baseline level of severity. Events with a missing severity during the treatment period will be considered treatment-emergent.
- Adverse events with a particular LLT will be classified as treatment-emergent if they first start on or after the first dose date/time in the treatment period (i.e., a patient has no pre-existing conditions with that lowest level term), or if the severity is greater than the pre-

treatment severity for that lowest level term. If a partial AE start date/time is present, the date/time will be compared as far as possible to the treatment start date/time in order to determine whether the event is treatment emergent or not. If there is any doubt, the event will be flagged as treatment emergent.

A follow-up emergent adverse event (FEAE) is defined as an event that first occurred or worsened in severity after the date of Visit 12 (that is, Week 52) or the ETV:

- The MedDRA LLT will be used when classifying AEs as follow-up emergent.
- For AEs that are ongoing at the date of Visit 12 or ETV, the maximum severity recorded for each LLT on or prior to the date of Visit 12 or ETV will be used as the follow-up baseline severity for that LLT.
- If a partial AE start date is present, the date will be compared as far as possible to the date of Visit 12 or ETV in order to determine whether the event is follow-up emergent or not. If there is any doubt, the event will be flagged as follow-up emergent, unless the same event was already counted as treatment-emergent during the treatment during a previous treatment period (Period 2 or Period 3).

Adverse events and TEAEs will be summarized and analyzed for the safety population for the Blinded Treatment Period (Period 2). The comparisons between treatment groups will be conducted using Fisher's exact test.

Adverse events and TEAEs will be summarized for the Open-label Treatment Population for the Open-label Treatment Period (Period 3).

The following will be presented for the Blinded and Open-label Treatment periods respectively:

- An overall summary of AEs including the number and percentage of patients who experienced TEAE, TEAE by maximum severity, death, SAE, TEAE related to study drug, discontinuations from the treatment due to an AE, and TEAEs of special interest
- TEAE by SOC and PT
- TEAE by PT
- TEAEs possibly related to study drug (evaluated by the investigator), by SOC and PT
- TEAE by maximum severity, SOC, and PT.

In addition, the overall summary of AEs will also be presented for the patients who received at least one dose of ixekizumab, during the Combined Treatment Period (Blinded Treatment Period [Period 2] and Open-label Treatment period [Period 3]). The summary table includes the number and percentage of patients who experienced TEAE, TEAE by maximum severity, death, SAE, TEAE related to study drug, discontinuations from the treatment due to an AE, and TEAEs of special interest, during the Combined Treatment Period.

Follow-up emergent adverse events will be summarized for the follow-up population for the Post-Treatment Follow-up Period (Period 4):

- FEAE by PT

In general, for all AE related summaries, the number and percentage of patients experiencing the events will be presented by treatment group. The events will be ordered by decreasing frequency in the total ixekizumab group, followed by Q2W and placebo in the Blinded Treatment Period and for total ixekizumab group in the Open-label Treatment Period within SOC and/or PT for sorting. For events that are gender-specific (as defined by MedDRA), the denominator and computation of the percentage will include only patients from the given gender.

A by-patient listing of all AEs will be provided.

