4.1. Overview of Study Design

Study I1F-MC-RHBQ (RHBQ) is a Phase 3, multicenter, randomized, double-blind, placebo-controlled, parallel-group, outpatient study examining the efficacy and safety of ixekizumab as compared to placebo in patients with moderate-to-severe genital psoriasis. The study consists of 4 periods:

- **Period 1: Screening Period** (Visit 1 and Visit 1A) will assess patient eligibility and start e-diary data collection, occurring approximately 7 to 30 days prior to Period 2 (baseline; Week 0; Visit 2).
- **Period 2: Blinded Treatment Period** will occur from Week 0 (Visit 2) up to Week 12 (Visit 7). Patients will be randomized to ixekizumab or placebo in a 1:1 ratio. Two injections of ixekizumab 80 mg SC (total dose of 160 mg) or 2 injections of placebo SC, respectively, will be given at Week 0 (Visit 2). From Week 2 through Week 10 patients will receive ixekizumab 80 mg Q2W SC or placebo Q2W SC (Section 6.1).
- **Period 3: Open-Label Treatment Period** will occur from Week 12 (Visit 7) up to Week 52 (Visit 12). At Week 12 (Visit 7) 1 injection of ixekizumab 80 mg SC and 1 injection of placebo SC (total dose of ixekizumab 80 mg) will be given to patients who were randomized to ixekizumab in Period 2; and 2 injections of ixekizumab 80 mg SC (total dose of ixekizumab 160 mg) will be given to patients who were randomized to placebo in Period 2. During the remainder of Period 3, patients will receive ixekizumab 80 mg Q4W dosing with an option to step-up to Q2W dosing starting at Week 24 through Week 40 (at Visit 9 [Week 24], Visit 10 [Week 28], or Visit 11 [Week 40]) (Section 6.1). This open-label period will allow evaluation of long-term efficacy and safety of ixekizumab through 1 year (52 weeks).
- **Period 4: Post-Treatment Follow-Up** (Visit 801 through Visit 803) is for safety monitoring after treatment discontinuation for any patient receiving at least 1 dose of investigational product. Once patients complete study treatment or discontinue study treatment early, patients will complete the Post-Treatment Follow-Up (Period 4). For patients who have entered Period 4, psoriasis therapy is allowed, as determined appropriate by the investigator. This period occurs from the last treatment period visit or early termination visit (ETV) up to a minimum of 12 weeks following that visit.

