6.1. Treatments Administered

The Blinded Treatment Period (Period 2) involves a comparison of ixekizumab 80 mg Q2W (starting dose of 160 mg) and placebo Q2W. All doses are administered via SC injection.

All patients assigned to ixekizumab 80 mg Q2W regimen will receive a starting dose of 160 mg ixekizumab as 2 SC injections. The placebo group will receive 2 SC injections of placebo at this visit as well, to maintain the blind.

For training purposes, the starting dose of 160 mg (two 80-mg SC injections) will be administered at the clinic at Week 0 (Visit 2). The first injection will be administered by clinical staff, and the second injection will be administered by the patient or the patient's caregiver while under supervision of clinical staff. Subsequent injections of investigational product will be administered by the patient or the patient's caregiver unsupervised by the clinical staff, regardless of whether there is a study visit scheduled except at Visit 7 (Week 12). At Visit 7 (Week 12), the 2 injections will be administered by the patient or the patient's caregiver supervised by the clinical staff to allow for vital sign monitoring (Section 8.4.2). It is recommended that all subsequent injections be administered outside the trial site, preferably at the patient's home.

A dose of investigational product will consist of 1 SC injection of ixekizumab or placebo. Possible injection sites include the abdomen (upper left, upper right, lower left, or lower right quadrant [with the umbilicus being the center]), left or right thigh, and left or right upper arm. If the upper arm is utilized as the injection site, the injection must be administered by a caregiver. The injection site should not be in a psoriatic lesion. On days when multiple injections will be administered, the injection sites should be in different areas (note the abdomen has 4 possible injection areas).

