9.6.1. Adverse Events

Adverse events are classified based upon the Medical Dictionary for Regulatory Activities (MedDRA). A TEAE is defined as an event that first occurred or worsened in severity after the first dose of study treatment and on or prior to the date of the last visit within the treatment period. Both the date/time of the event and the date/time of the dose (ie, injection) are considered when determining TEAEs. For each TEAE, the severity is recorded according to the patient's or physician's perceived severity of the event (mild, moderate, or severe). A follow-up emergent adverse event (FEAE) is defined as an event that first occurred or worsened in severity after the date of Week 52 (Visit 15) or the ETV. For events that are gender specific, the denominator and computation of the percentage will only include patients from the given gender.

An overall summary of AEs will be provided for each treatment period. TEAEs, SAEs including deaths, AEs that led to investigational product discontinuation, and AEs by maximum severity and relationship to investigational product will be summarized by MedDRA system organ class (SOC) and preferred term (PT). TEAEs will also be summarized by PT sorted by decreasing frequency within SOC for all TEAEs, TEAEs by maximum severity, and TEAEs considered possibly related to investigational product.

FEAEs (all, by maximum severity, and FEAEs possibly related to investigational product by the investigator), SAEs including deaths, AEs that lead to study discontinuation will be summarized by MedDRA SOC and PT or by PT for the Post-Treatment Follow-Up Period (Period 4).

In addition to general safety parameters, safety information on specific topics of special interest will also be presented. Potential AESIs will be identified by a standardized MedDRA query (SMQ) or a Lilly defined MedDRA PT listing. The details of the AESIs will be defined in the SAP.

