6.1.2. Baseline Definition

Unless otherwise specified, for efficacy and health outcomes analyses in the Blinded and Open-label Treatment periods, baseline will be defined as the last available value before the first injection of the investigational product. In most cases, this will be the measurement recorded at Week 0 (Visit 2). For efficacy measures, if the patient does not take any injection, the last available value on or prior to randomization date will be used.

Unless otherwise specified for safety analyses in the Blinded Treatment Period, baseline will be defined as the last available value before the first injection of the investigational product. In most cases, this will be the measurement recorded at Week 0 (Visit 2). For safety analyses using a baseline period, the baseline period is defined as the time from Visit 1 to the date/time of the first injection.

Unless otherwise specified, the baseline for safety analyses in the Open-label Treatment Period is defined as the last non-missing assessment on or prior to Week 12 (Visit 7) and prior to the first injection of the open-label investigational product at Visit 7.

Unless otherwise specified, the baseline for safety analyses in the Post-Treatment Follow-up Period is defined as the last non-missing assessment on or prior to Week 52 (Visit 12) or ETV.

For each Genital Psoriasis Symptoms Scale (GPSS) item score and the total score, the baseline for efficacy analyses in the Blinded and Open-label Treatment Period is defined as the average of 4 or more non-missing assessments collected during the last 7 consecutive days, prior to the date of the first injection, that is, the sum of the assessments divided by the number of days on which the assessment is completed. When there are <4 non-missing assessments in the 7-day window, the window will be extended towards the date of Visit 1, until 4 daily non-missing assessments are found. However, if there are not at least 4 non-missing assessments collected prior to the date of the first injection, the baseline will be designated as missing.

For Genital Psoriasis Sexual Impact Scale (GPSIS) subscale scores and Sexual Frequency Questionnaire (SFQ) item scores, the baseline for efficacy analyses in the Blinded and Open-label Treatment Period is defined as the last non-missing assessment collected prior to the date of the first injection.

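### The Period 2 adverse-event window closes on a date (Visit 7) but Period 3 opens at an injection time that same day, so same-day reactions to the placebo arm's first ixekizumab dose are counted in both periods, including the placebo column.

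*SAP*

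**What the plan says.** **Closing boundary.** SAP 6.15.2 closes each treatment period's window at a calendar date: "on or prior to the date of the last visit within the defined treatment period". Protocol 9.6.1 has the same bound: "on or prior to the date of the last visit within the treatment period".

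**Opening boundary.** SAP 6.15.2 classifies events as treatment-emergent "if they first start on or after the first dose date/time in the treatment period", or if they exceed the pre-treatment severity. This boundary carries a clock time.

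**Linking sentences.** SAP 6.15.2 adds "Both the date/time of the event and the date/time of the dose (that is, injection) are considered when determining TEAEs", and then "Treatment-emergent AEs will be assigned to the respective study periods in which they are considered treatment-emergent".

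**Visit 7.** Protocol 4.1 and SAP 5.1 end Period 2 and begin Period 3 at this same visit. Dosing takes place there: "At Visit 7 (Week 12), the 2 injections will be administered by the patient", under staff supervision (protocol 6.1). Protocol 4.1 gives the placebo arm's dose at this visit: "2 injections of ixekizumab 80 mg SC (total dose of ixekizumab 160 mg) will be given to patients who were randomized to placebo". The ixekizumab arm receives one active and one placebo injection.

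**Period 3 safety baseline.** SAP 6.1.2 does cut this at the injection: the last assessment on or before Week 12 "and prior to the first injection of the open-label investigational product at Visit 7".

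**The concern.** One boundary is a date and the other a time, and both fall on the Visit 7 date. From the injection until midnight, both windows are open. Events in those hours are the ones most plausibly caused by the injection, and in the placebo arm the drug injected is ixekizumab.

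Protocol 9.6 focuses the primary safety analysis on ixekizumab versus placebo in Period 2. Injection-site reactions and allergic reactions are named events of special interest (protocol 8.2.2), and SAP Table RHBQ.6.6 compares them in Period 2 by Fisher's exact test. Adding ixekizumab reactions to the placebo column pulls that comparison towards no difference. The same event is also reported again in Period 3.

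Vital signs have a related gap. Protocol 8.4.2 schedules a blood pressure and pulse reading about 1 hour after the Visit 7 dose. The Period 2 high and low categories in SAP 6.15.5 take in all post-baseline readings, with no cut at that dose.

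**Working it through.** The plan gives no figure on this point to reproduce, so the check is mainly a reading of the rules together.

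**Step 1: one worked case.** A placebo-randomised patient is injected at Visit 7 at 10:00 and has a first-ever injection-site reaction at 14:00 the same day (times are illustrative).

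| Test | Period 2 | Period 3 |
|---|---|---|
| Opens | First dose at Week 0: met | Visit 7 injection, 10:00: met |
| Closes | Date of last Period 2 visit, which is the Visit 7 date: met | Date of last Period 3 visit: met |
| Treatment-emergent? | Yes | Yes |

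**Step 2: look for a rule that removes the event from Period 2.**
- The sentence on event and dose times is applied through the bullets beneath it. Those use the first dose of a period to set pre-treatment severity and to decide whether an event started after that dose. None uses the next period's dose to close the earlier period.
- The assignment sentence sends an event to the periods in which it is treatment-emergent. It has no tie-break when there are two.
- For partial start dates or times, doubt is resolved by flagging the event as treatment-emergent. Which period takes it is not stated.

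No rule removes the event from Period 2.

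**Step 3: compare other boundaries in the SAP.**
- The Period 3 safety baseline (6.1.2) is cut before the Visit 7 injection.
- Concomitant therapy (6.8.2) has a same-day rule: a therapy that starts and ends on the first day of Period 3 treatment belongs to Period 3.
- Follow-up emergent events (6.15.2) begin after the Visit 12 date, so they do not overlap with Period 3.

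Only the Visit 7 boundary for adverse events lacks such a rule.

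**Step 4: scale.** The documents give no same-day reaction rate, so 2%, 5% and 10% are assumptions. With 73 placebo patients (SAP 5.3), all assumed to reach Visit 7 and enter Period 3:
- 73 × 0.02 = 1.46, about 1.5 patients
- 73 × 0.05 = 3.65, about 3.7 patients
- 73 × 0.10 = 7.3 patients

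**Step 5: sensitivity of the test.** All counts below are hypothetical; two-sided Fisher's exact test, 73 per arm.

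| Ixekizumab v placebo, patients with event | p |
|---|---|
| 11 v 3 (no Visit 7 post-dose events) | 0.046 |
| 11 v 5 (2 added to placebo only) | 0.184 |
| 11 v 7 (4 added to placebo only) | 0.451 |
| 13 v 5 (2 added to each arm) | 0.076 |
| 16 v 3 (clearer starting difference) | 0.002 |
| 16 v 5 (2 added to placebo only) | 0.017 |

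A handful of patients can move a borderline comparison. A clear difference survives the same change, and equal additions to both arms do less damage than additions to placebo alone.

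**The case against.** The strongest reply is that SAP 6.15.2 already takes event and injection times into account, and that for Period 3 the relevant first dose is the Visit 7 injection. A timed reaction after it is therefore a Period 3 event, and the baseline and concomitant-therapy rules suggest that the injection was the intended boundary. A sensible programmer might well cut there.

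Part of this stands. The event is treatment-emergent in Period 3. A reader might infer from the closing date alone that these reactions count as placebo events instead of Period 3 events; the documents do not support that. But qualifying for Period 3 does not take the event out of Period 2, and the intended cut is not written down.

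Other limits also stand:
- Only patients who continue into Period 3 are injected at Visit 7, not everyone randomised.
- The ixekizumab arm also gets two injections that day, so it can gain events too, although not from a first exposure.
- The tables count patients, so a placebo patient already counted for the same term adds nothing.
- These comparisons carry no multiplicity adjustment (SAP 6.4), and crossing 0.05 decides no formal claim.
- SAP 6.15.3.1 lets the ixekizumab program safety analysis plan supersede the SAP when term lists or analyses for special safety topics change. That plan is not available here, so whether it sets period windows is unknown.
- Protocol 9.6.3 already summarises pre-dose and post-dose vital signs at Week 12. That does not say whether the post-dose reading enters the Period 2 high and low categories.

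**Conclusion.** The rule as written is defective, within limits. A new adverse event after the injection on the Visit 7 date meets the definitions for both periods. For placebo-randomised patients it is counted in the placebo column of the primary safety comparison as well as in Period 3.

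The likely effect is a small bias towards no difference, confined mainly to injection-site and hypersensitivity reactions. Its size is unknown. The range of about 1.5 to 7.3 placebo patients rests on an assumed same-day rate of 2% to 10% and on all 73 being dosed at Visit 7. It is an upper view of the net effect, because it ignores the offset from the ixekizumab arm and patients already counted.

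A reader might infer from the first rows of the Fisher table that a real safety difference would be hidden. The documents do not support that: the starting counts are hypothetical and chosen near the 0.05 line, and those rows add events to one arm only. The point is worth correcting because the text allows the misattribution and the correction is cheap, not because a material distortion has been shown.

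**What to change.** In SAP 6.15.2, for patients who enter Period 3:
- End the Period 2 treatment-emergent window immediately before the date and time of the first Period 3 injection at Visit 7. Patients who do not enter Period 3 keep the existing closing date.
- Assign events that start at or after that injection on the Visit 7 date to Period 3 only.
- Pre-specify one default for Visit 7-date events with no recorded time, applied to all event types and both arms. A default limited to injection-site and hypersensitivity reactions would also move events that preceded the injection, and would do so selectively.

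In SAP 6.15.5, apply the same cut so that the Visit 7 post-dose blood pressure and pulse readings do not enter the Period 2 high and low categories.

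The cost is a sentence or two in each section and the matching programming specification. The treatment-emergent rule already refers to event and injection times. The one judgement needed is the default for untimed events, which should be fixed before unblinding.

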6.10 Efficacy Analyses	
Updated derivations of GPSS item and total scores at Week 1 (Visit 3), Week 2 (Visit 4), Week 4 (Visit 5), Week 8 (Visit 6), and Week 12 (Visit 7).
 
Updated derivations of GPSS item and total scores at each calendar week in the Blinded Treatment Period.
 
Updated the scoring scheme for GPSIS subscale scores.
 
Updated derivations of GPSIS subscale scores at Week 1 (Visit 3), Week 2 (Visit 4), Week 4 (Visit 5), Week 8 (Visit 6), and Week 12 (Visit 7).
 
Updated derivations of GPSIS subscale scores at each calendar week in the Blinded Treatment Period.
 
Updated derivations of SFQ item scores at Week 1 (Visit 3), Week 2 (Visit 4), Week 4 (Visit 5), Week 8 (Visit 6), and Week 12 (Visit 7).
 
Updated derivations of SFQ item scores at each calendar week in the Blinded Treatment Period.
 
Added exploratory analyses on change from baseline and/or a meaningful improvement from baseline for GPSS, GPSIS, and SFQ at each calendar week in the Blinded Treatment Period.
 
Added exploratory analyses on GPSS Itch score for the change from baseline analyses during the first 14 days, to examine the rapid improvement from baseline in the Blinded Treatment Period.
 
Added exploratory analyses on the association of absence/presence of genital fissure/ulcer/erosion with sPGA of genitalia at Week 12.
 
Added exploratory analyses on the association of absence/presence of genital fissure/erosion/ulcer with measures of quality of life (SF-36 MCS, DLQI, GPSIS Subscales, and SFQ items at Week 12.
 
Added exploratory analyses on the association of absence/presence of perianal/gluteal cleft psoriasis with measures of quality of life (SF-36 MCS, DLQI, GPSIS Subscales, and SFQ items at Week 12.
 
Added exploratory analyses on the association of absence/presence of facial psoriasis with measures of quality of life (SF-36 MCS, DLQI, GPSIS Subscales, and SFQ items at Week 12.

6.15.1 Extent of Exposure	
Added the duration of exposure to ixekizumab treatment for combined treatment period.

Section	Summary of Changes
6.15.2 Adverse Events	Added the overall summary of AEs for combined treatment period.

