6.15.3. Deaths, Other Serious Adverse Events, and Other Notable Adverse Events

By-patient listings of deaths, serious AEs (SAEs), and AEs leading to discontinuation will be provided, respectively. All deaths will be included, regardless of the investigator's or the sponsor's judgment about causality, including:

- any deaths occurring during participation in the study in the database for which data are being presented
- any deaths occurring after a patient leaves (is discontinued from or completed) the study in the database for which data are being presented if:
 - the death is the result of a process initiated during the study, regardless of when it actually occurred, or
 - the death occurs during the Period 4 after discontinuation of study drug.

An SAE is any AE that results in one of the following outcomes: death, life-threatening, initial or prolonged hospitalization, disability or permanent damage, congenital anomaly or birth defect, or any other serious/important medical events.

The following summary tables (including treatment group comparison) will be provided for the safety population for Period 2 and the Open-label Treatment Population for Period 3:

- SAEs by PT

- AEs that lead to treatment discontinuation (including death) by PT

A follow-up emergent serious adverse event (FESAE) is defined as an SAE that first occurred or worsened in severity after the date of Visit 12 (that is, Week 52) or the ETV. The following summary tables will be provided for the follow-up population for the Post-Treatment Follow-up Period (Period 4):

- FESAE by PT
- FEAEs that lead to treatment discontinuation (including death) by PT.

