6.15.3.1. Special Safety Topics including Adverse Events of Special Interest

Safety information on special topics including AEs of special interest (AESI) will be presented by treatment group and by study period. [Table RHBQ.6.6](#) provides the definitions/derivations and analyses methods (including analyses, summaries and by-patient listings) of special safety topics including AESIs.

Potential AESIs will be identified by a standardized MedDRA query (SMQ) or a Lilly-defined MedDRA PT listing. Preferred terms within an SMQ will be classified as broad and narrow. In the Lilly-defined MedDRA PT listings, Lilly has provided the broad and narrow classifications. The Lilly-defined broad terms are for a more sensitive search of potential events of interest and the Lilly-defined narrow terms are for a more specific search. Therefore, the summaries will include the classifications of broad term (same as pooling narrow and broad terms together) and narrow term.

In the event that the listing of terms or analyses changes for a special safety topic, it will be documented in the IXE PSAP which will supersede this document; it will not warrant an amendment to the individual study SAP.

Fisher's exact tests will be used to compare the treatment groups for the safety population during the Blinded Treatment Period (Period 2).

For the Open-label Treatment Period (Period 3) and the Post-Treatment Follow-up Period (Period 4), summaries will be provided using the Open-label Treatment Population and the Post-Treatment Follow-up Population, respectively.

Table RHBQ.6.6. Definitions and Analyses of Special Safety Topics including Adverse Events of Special Interest

Special Safety Topic	Definition / Derivation	Analysis / Summary / Listing

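### As written, the combined-period AE summary of ixekizumab-treated patients includes the placebo arm's Week 0-12 TEAEs and SAEs, which precede their first ixekizumab dose

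*SAP*

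**What the plan says.** SAP 6.15.2 adds an overview of the two treatment periods together: "the overall summary of AEs will also be presented for the patients who received at least one dose of ixekizumab, during the Combined Treatment Period". It defines that period as the Blinded plus the Open-Label Treatment Period. Besides any TEAE, the rows are "TEAE by maximum severity, death, SAE, TEAE related to study drug, discontinuations from the treatment due to an AE, and TEAEs of special interest, during" that same period.

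The rules that decide which events count are these:

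- **TEAEs (6.15.2).** At lowest-level-term (LLT) level, events are treatment-emergent if they "first start on or after the first dose date/time in the treatment period", or if they exceed the worst severity recorded before that dose.
- **SAEs (6.15.3).** "An SAE is any AE that results in one of the following outcomes", followed by the list of outcomes. Treatment emergence is not required.
- **Layout (6.15.2).** "In general, for all AE related summaries, the number and percentage of patients experiencing the events will be presented by treatment group".
- **Special-interest events (6.15.3.1).** If the term lists or analyses for a special safety topic change, "it will be documented in the IXE PSAP which will supersede this document".

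Section 6.1.2 gives safety baselines for Periods 2, 3 and 4 and none for the combined period.

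Two other parts of the SAP use the first ixekizumab dose as their starting point. Combined-period exposure in 6.15.1 runs from that dose. The immunogenicity baseline in 6.16.1.3 (Table RHBQ.6.8) is Week 12 for the placebo arm. The Revision History (Section 3) lists the exposure and AE additions in the same SAP version: "Added the duration of exposure to ixekizumab treatment for combined treatment period" and "Added the overall summary of AEs for combined treatment period".

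**The concern.** Limiting the table to patients who received ixekizumab suggests that it is meant to describe events on ixekizumab, and readers will take it that way. The stated rules also admit what happened to the placebo arm before any active drug. An any-event percentage can only rise as a result. The maximum-severity rows can shift upward, so the mild row may fall when a patient's worst event becomes a moderate or severe one from the placebo phase.

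Not every row is exposed. A patient who dies or stops treatment for an AE while on placebo never receives ixekizumab and so never enters the table. An AE that starts on placebo and leads to discontinuation after Week 12 does enter.

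**Working it through.** The plan states no figure on this point, so there is none to reproduce. The check is a reading of the rules, followed by arithmetic on the planned design.

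**1. The rules applied to one patient.** Take a placebo-randomised patient who continues past Week 12.

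- Population: the first ixekizumab is given at Week 12 (SAP 5.1), so the patient qualifies.
- Window: Period 2 is part of the combined period, so Weeks 0-12 are included.
- TEAE start: the rule says first dose, without naming ixekizumab. Placebo counts as a dose. The protocol's Appendix 1 includes placebo in investigational product, protocol 9.6.1 starts TEAEs at the first dose of study treatment, and the SAP's Safety Population uses that term for both arms. The start is therefore the Week 0 placebo injection.
- SAEs: no emergence condition applies, so an SAE in Weeks 0-12 counts.

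The 6.15.1 exposure formula had to specify the first ixekizumab dose within the combined period, so that period does not itself begin at that dose. The AE paragraph has no such qualifier.

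**2. Share of the window that is placebo time.** Inputs: 73 per arm (SAP 5.3), 12 blinded weeks and 40 open-label weeks.

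- Full retention: 73 × 12 = 876; 2 × 73 × 52 = 7592; 876 / 7592 = 11.5%. For one placebo-to-ixekizumab patient it is 12/52 = 23%.
- Dropout before Period 3 of 10% / 20% (assumed; ixekizumab dropouts contribute 6 weeks on average and placebo dropouts are not in the table): placebo arm only, 10.9% / 10.3%; both arms, 11.5% / 11.4%; ixekizumab arm only, 12.1% / 12.7%.
- 10% / 20% of both arms leaving at Week 32: 12.0% / 12.5%.

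No planned statistic uses this share. It only describes the window.

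**3. Effect on an any-event percentage (illustration).** The documents give no AE risks. Assume equal arm sizes and the same hazard on placebo and ixekizumab, and let *p* be the 40-week risk after starting ixekizumab. The rise in the placebo-to-ixekizumab column is the chance of an event in Weeks 0-12 and none afterwards. A single pooled column rises by half of that.

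| Assumption | Column rise | *p* = 3%: column / pooled | *p* = 60%: column / pooled |
|---|---|---|---|
| Constant hazard | (1−*p*)·*q*, with *q* = 1−(1−*p*)^(12/40) | 0.88 / 0.44 | 9.61 / 4.81 |
| Gamma frailty, variance 1 | (1−*p*) − 1/(1+1.3*L*), with *L* = 1/(1−*p*)−1 | 0.87 / 0.43 | 6.10 / 3.05 |
| All risk in the 12 weeks after each treatment start | *p*(1−*p*) | 2.91 / 1.45 | 24.0 / 12.0 |

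Values are percentage points. For the constant-hazard row, *q* = 0.91% at *p* = 3% and 24.03% at *p* = 60%. The third row peaks at *p* = 50%, where the pooled rise is 0.5 × 0.5 / 2 = 12.5 points. With constant hazards, *p* = 60% and a placebo hazard 0.5 or 1.5 times the ixekizumab hazard, the pooled rise is 2.57 or 6.76.

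If the 12-week placebo risk *a* and the 40-week open-label risk *b* are instead chosen separately and taken as independent, the pooled rise is *a*(1−*b*)/2. It runs from 0.20 × 0.40 / 2 = 4 points to 0.60 × 0.60 / 2 = 18 points over *a* = 20-60% and *b* = 40-60%. For SAEs with *a* = 0.5-3% and *b* = 4%, 73·*a*·0.96 gives about 0.4 to 2 extra patients.

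**The case against.** The strongest reply is that the start date for this table is undefined, and that an undefined date is not the same as one fixed at the placebo injection. Section 6.1.2 has no combined-period baseline, and its first-injection wording belongs to the Period 2 paragraph. The neighbouring exposure text uses the same period and the same patients, was added in the same revision, and starts at first ixekizumab. A programmer might simply carry that date over.

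This stands as evidence of intent. It does not change the rule: 6.15.2 has its own TEAE start, and once the treatment period is the combined one, that rule points to the Week 0 injection. No sentence extends the exposure date to the AE table.

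Showing the table by treatment group would leave the ixekizumab column unchanged and make the source of the extra events visible. It would also concentrate the whole effect in the placebo-to-ixekizumab column, at twice the pooled size, without removing any event.

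Two limits are accepted. The percentage-point figures depend entirely on assumed risks. The special-interest row cannot be settled from the SAP alone, because the programme safety plan can override it.

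**Conclusion.** The concern holds, as a minor point. Under the stated rules, a table presented as ixekizumab-treated patients counts TEAEs, related TEAEs and SAEs that arose on placebo. On-ixekizumab events were probably intended, but the text does not say so.

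Placebo time is 11.5% of the window with full retention and 10.3% to 12.7% in the dropout cases computed. With equal constant hazards, the pooled any-event percentage is overstated by 0.4 points (3% risk) to 4.8 points (60% risk). Clustering of events in the same patients lowers the upper figure to about 3.1, and front-loaded risk raises it to 12 or slightly more. These figures are illustrations and do not bound the effect.

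The table is descriptive and carries no test. The separate Period 2 and Period 3 tables and the by-patient AE listing are unaffected.

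**What to change.** Add to SAP 6.15.2 that, for the combined-period summary, the baseline, the pre-treatment severity and the start of the TEAE and SAE windows are all the patient's first ixekizumab injection, which is Week 12 for placebo-randomised patients. Placebo-phase events are then excluded. The same text could also say how to count an AE that starts on placebo and leads to discontinuation after Week 12, and whether the table is pooled or split by group. Those two points are drafting detail.

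The cost is one or two sentences and one derivation flag. No new data are needed, and the Period 2 and Period 3 tables do not change. There is one downside to record: a placebo-phase event that recurs on ixekizumab in the same LLT at the same severity would no longer count as treatment-emergent in this table.
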